## 2. OBJECTIVES AND ENDPOINTS

Primary Objective	Co-Primary Endpoints

To assess the safety of switching to B/F/TAF in virologically suppressed participants unable/unwilling to continue on CAB+RPV IM injections or wishing to switch to oral therapy through Week 12

	

Proportion of participants experiencing treatment-emergent Grade 3 or 4 study drug-related adverse events through Week 12

Proportion of participants experiencing treatment-emergent Grade 3 or 4 laboratory abnormalities through Week 12

Secondary Objectives	Secondary Endpoints

To assess the pharmacokinetics of BIC, CAB, and RPV after switching to B/F/TAF from CAB+RPV

To assess the efficacy and persistence of B/F/TAF after switching from CAB+RPV

To assess the safety of B/F/TAF after switching from CAB+RPV through Week 24

To evaluate treatment satisfaction of switching to B/F/TAF from CAB+RPV

	

Plasma concentrations of BIC, CAB, and RPV at Day 1, Weeks 4, 12, and 24, as appropriate

Proportion of participants with HIV-1 RNA <math>\geq 50</math> copies/mL at Weeks 12 and 24 (missing = excluded and discontinuation = failure)

Number and proportion of participants with B/F/TAF discontinuation by Weeks 12 and 24

Proportion of participants experiencing treatment-emergent grade 3 or 4 laboratory abnormalities through Week 24

Change in HIV treatment satisfaction (HIVTSQc) score at Week 4

Exploratory Objective	Exploratory Endpoints

To understand PWH experience with injectable and oral therapies for HIV treatment

To evaluate reasons for switching to B/F/TAF from CAB+RPV

	

Participant reported experiences with CAB+RPV, preferences for injectable and oral therapies

Participant-reported reasons for switching to B/F/TAF

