#### **6.4.1. Management of Virologic Rebound**

Participants experiencing, at any post-Day 1 visit, a rebound in HIV-1 RNA to  $\geq 50$  copies/mL, will be considered to have virologic rebound. At any visit with HIV-1 RNA  $\geq 50$  copies/mL, if the HIV-1 RNA is  $\geq 50$  and  $< 200$  copies/mL, a reflex HIV-1 RNA repeat test will be conducted on stored plasma samples, if available. If the repeat (reflex) result is  $< 50$  copies/mL, no further action is required. If the repeat result is  $\geq 50$  copies/mL, participants will be asked to return to the clinic for a scheduled or unscheduled blood draw (2 to 3 weeks after the date of the original test that resulted in HIV-1 RNA VR) for confirmation of VR.

- If VR is confirmed and HIV-1 RNA is  $\geq 200$  copies/mL, a plasma sample from the VR confirmation visit is the primary sample tested for HIV-1 PR, RT, and IN genotypic and phenotypic resistance. After a participant's first post-Day 1 resistance test, additional testing is conducted on a case-by-case basis. Any participant may be discontinued at investigator's discretion or per local treatment guidelines.
- If no resistance to study drug is detected from the genotype or phenotype, the participant may remain on study drug and HIV-1 RNA test should be repeated at a new visit (within 2-4 weeks after date of test with HIV-1 RNA  $\geq 50$  copies/mL). Investigators should carefully evaluate the benefits and risks of remaining on study drug for each individual participant and document this assessment in the on-site medical record.
- For participants who are off study drug but remain on study, it will be the investigator's discretion to manage virologic rebound.

[Figure 2](#) describes the management of participants who experience virologic rebound.

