## **6.6. Assessments for Early Discontinuation From Study Intervention or From the Study**

If a participant discontinues study medication dosing (eg, as a result of an AE), every attempt should be made to keep the participant in the study and continue to perform the required study-related follow-up and procedures ([Section 3.3](#)). If this is not possible or acceptable to the participant or investigator, the participant may be withdrawn from the study. The participant will be requested to return for an early study ESDD visit. If it is not possible or acceptable to the participant or investigator to keep the participant in the study (after discussion of the benefits/risks with the investigator), the participant may be withdrawn from the study and be required to return to the study site for a 30-day follow-up visit ([Table 3](#)).

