Study Drug Accountability		X	X	X	X	X	X	
Study Drug Dispensation		X		X				
Observed Dosing		X	X	X				Participants must take their study drug in the clinic for observed dosing on Day 1, Week 4, and Week 12.

CBC = complete blood count; CD4+ = clusters of differentiation 4; DNA = deoxyribonucleic acid; DBS = dried blood spot; ESDD = early study drug discontinuation; GFR = glomerular filtration rate calculated using the Cockcroft-Gault equation; HBV = hepatitis B virus; HCV = hepatitis C virus; HIV-1 = human immunodeficiency virus type 1; HIVTSQs = HIV treatment satisfaction status questionnaire [quantitative]; HIVTSQc = HIV treatment satisfaction change questionnaire [quantitative]; RNA = Ribonucleic acid; PK = pharmacokinetic(s); TFV-DP = tenofovir diphosphate.

- a Evaluations to be completed within 42 days prior to Day 1 visit.
- b Participants will be dispensed study drug at the Day 1 visit; initiation of treatment with the study drug must take place in the clinic for observed dosing at Day 1 visit.
- c All study visits are to be scheduled relative to the Day 1 visit date. Visit windows are  $\pm 2$  days of the protocol-specified date through Week 12,  $\pm 6$  days of the protocol-specified date for Week 24. For the purpose of scheduling a 30-day follow-up visit, a  $\pm 6$ -day window may be used. Those participants who prematurely discontinue study drug and continue in the study through at least one subsequent visit after the early study drug discontinuation visit will not be required to complete the 30-day follow-up visit.
- d Only applies to participants who miss the Week 24 visit, and must be completed within 30 days of discontinuing study drug.
- e Early study drug discontinuation visit to occur within 72 hours of last dose of study drug.
- f Chemistry profile: alkaline phosphatase, AST, ALT, total bilirubin, direct and indirect bilirubin, total protein, albumin, bicarbonate, BUN, calcium, chloride, creatinine, glucose, potassium, and sodium.
- g For any post-Day -1 visit, if the HIV-1 RNA value is  $\geq 50$  copies/mL, a retest should be performed at a scheduled or unscheduled visit 2-4 weeks after the date of the original test.

- h Hepatitis B virus surface Antigen (HBsAg), Hepatitis B core antibody (HBcAb), and Hepatitis C virus (HCV) serologies (reflex HCV RNA is performed in participants with positive HCV Ab serology)

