3.7.3. PK Analysis Visits

For PK analysis, the nominal visit as recorded on the CRF will be used when data are summarized by visit.

Any data relating to unscheduled visits will not be assigned to a particular visit or time point and in general will not be included in by-visit summaries. However, the following exceptions will be made:

- An unscheduled visit prior to the first dosing of study drug may be included in the calculation of the baseline value, if applicable.

3.7.4. Selection of Data in the Event of Multiple Records in an Analysis Visit Window

Depending on the statistical analysis method, single values may be required for each analysis window. For example, change from baseline by visit usually requires a single value, whereas a time-to-event analysis would not require 1 value per analysis window.

If multiple valid, nonmissing measurements exist in an analysis window, records will be chosen based on the following rules if a single value is needed:

- For baseline, the last nonmissing value on or prior to the B/F/TAF will be selected, unless specified differently. If there are multiple records with the same time or no time recorded on the same day, the baseline value will be the average of the measurements for continuous data, or the measurement with the lowest severity for categorical data.
- For postbaseline values:
 - The record closest to the nominal day for that visit will be selected with the exception of viral load, CD4 cell counts, and CD4%, in which the latest record will be selected.
 - If there are 2 records that are equidistant from the nominal day, the later record will be selected.

- If there is more than 1 record on the selected day, the average will be taken for continuous data (except for HIV-1 RNA, see below) and the worse severity will be taken for categorical data.
- For postbaseline HIV-1 RNA, the latest (considering both date and time) record(s) in the window will be selected.
 - If both “HIV-1 RNA COBAS 6800” and “HIV RNA REPEAT COBAS” (ie, the HIV-1 RNA result obtained from an additional aliquot of the original sample) are available with the same collection time, the results from the “HIV RNA REPEAT COBAS” will be selected for analysis purposes; otherwise, if there are multiple “HIV-1 RNA COBAS 6800” records with the same collection time, the geometric mean will be taken for analysis purposes.

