6. EFFICACY ANALYSES

Efficacy data will be summarized for the participants in the FAS. For the FAS, all efficacy data, including data collected after the last dose of study drug, will be included, unless specified otherwise.

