6.2. Analysis of the Secondary Efficacy Endpoints

6.2.1. HIV-1 RNA ≥ 50 or < 50 copies/mL at Weeks 12 and 24 as determined by Missing=Excluded and Discontinuation=Failure approach

Number and percentage of participants with HIV-1 RNA ≥ 50 copies/mL and < 50 copies/mL by visit will be analyzed using the following 2 methods for imputing missing HIV-1 RNA:

- Missing = Excluded (M = E):

In this approach, missing data will be excluded in the computation of the percentages (ie, missing data points will be excluded from both the numerator and denominator in the computation). The denominator for percentages at a visit is the number of participants in the FAS with nonmissing HIV-1 RNA value at that visit.

- Discontinuation = Failure (D = F):

In this approach, treatment discontinuation-as-failure analysis includes participants with at least one HIV-1 RNA value within an analysis window (see Table 3-1.) and participants who discontinued B/F/TAF before the lower bound of the analysis window. All participants who discontinued B/F/TAF before the lower bound of the analysis window will be classified in the category 'HIV-1 RNA ≥ 50 copies/mL' (ie, virologic failure). Missing data in the analysis window due to the other reasons will be excluded from both denominator and numerator for D = F analysis.

For both M = E and D = F analyses, the number and percentage of participants with HIV-1 RNA in the following categories will be summarized based on the FAS:

- < 50 copies/mL
 - < 20 copies/mL
 - < 20 copies/mL Not Detectable
 - < 20 copies/mL Detectable
 - 20 to < 50 copies/mL
- \geq 50 copies/mL
 - 50 to < 200 copies/mL
 - 200 to < 400 copies/mL
 - 400 to < 1000 copies/mL
 - \geq 1000 copies/mL
 - Discontinuation (only applicable to D = F analysis)

The proportion of participants with HIV-1 RNA < 50 or \geq 50 copies/mL as defined by the 2 different missing data imputation methods will be summarized using descriptive statistics. Their 2-sided 95% CIs of the proportion will be constructed using the Clopper-Pearson Exact method.

For the D = F analysis, results will be summarized for Weeks 12, 24 and all other visits up to Week 24. For the M = E analysis results will be summarized for Weeks 12, 24 and all other visits with available data through the study.

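### In the Week 12 and Week 24 D=F analysis, a participant who stops B/F/TAF inside the analysis window can be counted as suppressed on the strength of a sample drawn off drug or on another regimen

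*SAP*

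**What the plan says.** Protocol 2 defines the secondary efficacy endpoint as the proportion with HIV-1 RNA of at least 50 "copies/mL at Weeks 12 and 24 (missing = excluded and discontinuation = failure"). Protocol 8.5 names the M=E and D=F approaches but gives no rule for a stop inside a window. The SAP supplies the rules:

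- **Data scope (SAP 6):** "For the FAS, all efficacy data, including data collected after the last dose of study drug, will be included, unless specified otherwise".
- **Failure by discontinuation (SAP 6.2.1):** "All participants who discontinued B/F/TAF before the lower bound of the analysis window will be classified in the category" of at least 50 copies/mL, which the SAP also calls virologic failure.
- **Other participants (SAP 6.2.1):** anyone with at least one HIV-1 RNA value in the window is included, with no on-treatment condition. For the rest: "Missing data in the analysis window due to the other reasons will be excluded from both denominator and numerator for D = F analysis".
- **Choice of record (SAP 3.7.4):** "For postbaseline HIV-1 RNA, the latest (considering both date and time) record(s) in the window will be selected".
- **Windows (SAP Table 3-1):** Days 57 to 126 for Week 12 and Days 127 to 210 for Week 24.

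Elsewhere the SAP does restrict data to on-treatment values. CD4 (6.3.1) and participant-reported outcomes (9) stop one day after the last dose. HIV-1 RNA has no such limit. SAP 6.4 declares no departure from the protocol's efficacy analyses.

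The protocol expects follow-up after a stop. Section 6.6 says "every attempt should be made to keep the participant in the study and continue to perform the required study-related follow-up and procedures". Table 3 note c covers those who "prematurely discontinue study drug and continue in the study through at least one subsequent visit after the early study drug discontinuation visit". Section 6.4.1 adds: "For participants who are off study drug but remain on study, it will be the investigator's discretion to manage virologic rebound". Figure 2 note c foresees a new regimen while the participant stays on study.

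**The concern.** Each rule is reasonable alone. Together they leave a stretch of each window in which stopping B/F/TAF is not a failure by rule and the result may come from a sample taken after the drug was stopped. The endpoint is meant to describe B/F/TAF after the switch, under a label saying that discontinuation counts as failure. Suppression achieved by a different regimen could then be reported as a B/F/TAF success. This could happen even where the last sample tied to B/F/TAF showed viremia and the protocol already calls the participant a virologic failure.

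The case would not be visible in the D=F table, because its Discontinuation row holds only stops before the window. The persistence table would not show it either: SAP 6.2.2 uses the same 57-day and 127-day cut-offs, so an in-window stopper does not count as non-persistent at that time point.

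**Working it through.** The plan states no event count or power to reproduce, so the check covers the windows, the availability of off-drug samples, the scoring rule and the exact intervals.

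**1. Windows.** The bounds in SAP Table 3-1 follow from midpoints of the nominal days: (28 + 84)/2 = 56, so Week 12 starts on Day 57; (84 + 168)/2 = 126, so Week 24 starts on Day 127; 168 + 42 = 210.

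**2. Days on which a stop is not a failure by rule at that visit.**
- Before nominal Week 12: Days 57 to 83, 83 − 57 + 1 = 27 of 83 days (32.5%).
- Before nominal Week 24: Days 127 to 167, 167 − 127 + 1 = 41 of 167 days (24.6%).

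These are shares of calendar days, not probabilities.

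**3. Would an off-drug sample fall in the window?** Protocol Table 3 schedules HIV-1 RNA at ESDD, at scheduled visits and at the 30-day follow-up.
- A participant who stays on study has the Week 12 visit (84 ± 2 = Days 82 to 86) or the Week 24 visit (168 ± 6 = Days 162 to 174).
- For one who attends the follow-up, stop + 30 days is Day 87 to 113 for a stop on Days 57 to 83, and Day 157 to 197 for a stop on Days 127 to 167. Adding the 6-day allowance gives at most Day 119 and Day 203, still inside 126 and 210.
- Table 3 note g also asks for a retest 2 to 4 weeks after any value of at least 50. After a viremic ESDD sample that retest follows the stop.

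**4. The D=F rule applied to hypothetical stops, Week 24.**
- Stop on Day 126: failure, whatever is measured later.
- Stop on Day 130, 120 copies/mL at ESDD on Day 132, below 50 on a new regimen on Day 168: the Day 168 record is latest, so **scored below 50**.
- Stop on Day 130, no ESDD sample, below 50 on a new regimen on Day 168: **scored below 50**.
- Stop on Day 130, no sample in Days 127 to 210: not a stop before the window, so **excluded** on the most natural reading of the clause on other reasons.
- Stop on Day 130, below 50 at ESDD, at least 50 off drug on Day 168: scored at least 50, which fits the D=F label.

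The same happens at Week 12. A stop on Day 60 with 120 copies/mL on Day 62 and below 50 on a new regimen on Day 84 is scored below 50 at Week 12. It is a failure at Week 24, because Day 60 precedes Day 127.

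**5. Effect of one case.** Assume 35 participants, the other 34 below 50, and Clopper-Pearson limits as in SAP 6.2.1. With no events the upper limit is 1 − 0.025^(1/n).
- 0/35: 0%, upper limit 1 − 0.025^(1/35) = 10.0%.
- 0/34: 0%, upper limit 1 − 0.025^(1/34) = 10.3%.
- 1/35: 2.9%, lower limit 1 − 0.975^(1/35) = 0.1%, upper limit 14.9% (beta quantile).

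The second and third cases in step 4 are reported as 0/35, and the fourth as 0/34. Each would be 1/35 if counted as a failure.

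**The case against.** The strongest reply is that this is an explicit definition. Protocol 8 leaves detail to the SAP, SAP 6.2.1 says who fails, who is included and who is excluded, and SAP 6.2.2 uses the same bounds. The plan consistently treats reaching the window as reaching the visit. That explains the rule. It does not explain why a sample on another regimen should overrule a viremic ESDD sample under this label.

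Several further points stand:

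- A reader might infer that off-drug viremia scored as at least 50 is also an error, so that the bias runs both ways. The documents do not support this. The participant discontinued and is viremic, and a failure is what the D=F label promises.
- A reader might infer that every in-window stop should be a failure. Neither document says so, and a stopper suppressed at ESDD can fairly be scored on that value.
- The viremic-ESDD case is narrow: it needs viremia at ESDD, a new regimen and re-suppression before the last in-window sample. The cases without an ESDD value mostly need a required sample to be missed or late.
- Dates of new antiretrovirals are a weak basis for a rule. SAP 7.5.1 covers them only if collected, and SAP 3.6.1 imputes a missing start day as the first of the month.
- Disposition, reasons for discontinuation and post-study antiretrovirals are reported, so a careful reader could find a case by hand.

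**Conclusion.** Wrong as written, with low impact. The combination follows from the SAP's own text and needs no outside assumption: off-drug or new-regimen suppression can be reported as a B/F/TAF success in D=F, and an in-window stopper without a sample is probably dropped.

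Few or no participants are likely to be affected. One case decides between 0% and 2.9%, given about 35 evaluable participants and no other failures. The endpoint is secondary and descriptive, so no test, error rate or primary safety result is touched. M=E on all available data is a stated choice and is not at issue, and stops before the window are handled as labelled.

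A reader might want a probability that such a case occurs. The documents give no B/F/TAF discontinuation rate from which to compute one; the rates in Protocol 1.3 describe leaving CAB+RPV. The day shares in step 2 cannot stand in for it.

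**What to change.** In SAP 6.2.1, with a cross-reference in 3.7.4:

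1. In D=F, for a premature stop inside the window and before the Week 12 or Week 24 visit, a value drawn after B/F/TAF was stopped, other than at ESDD, cannot classify the participant as below 50. Classify as below 50 only if the last in-window value on B/F/TAF or at ESDD is below 50 and no later in-window off-drug value is 50 or more. Otherwise classify as at least 50. Base the flag on the last-dose date and the ESDD visit label, not on imputed antiretroviral start dates.
2. Count such a stop with no in-window on-drug or ESDD value as a failure in the Discontinuation row, and do not exclude it.
3. Leave completers and M=E as planned, label M=E as including off-treatment data, and add one supportive on-treatment table.
4. State whether commercial B/F/TAF counts as on-treatment, consistent with SAP 6.2.2.

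The ESDD timing passages must be reconciled because the rule relies on that visit: 72 hours from stopping or from notification (Protocol 6.6.1), 72 hours from the last dose (Table 3 note e), and 30 days from stopping (6.6.2).

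The cost is SAP wording, one date flag and one table, with no new data collection. The D=F rate may look slightly less favourable. D=F discontinuation failures may exceed the non-persistence count, which a footnote can explain. Where the last-dose date is itself imputed from visit or laboratory dates (SAP 3.7.1), the flag is less certain and the case should be footnoted.

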6.1. Efficacy Endpoints

The secondary efficacy endpoints of this study are:

- The proportion of participants with HIV-1 RNA ≥ 50 copies/mL at Weeks 12 and 24 as determined by Missing = Excluded (M = E) and Discontinuation = Failure (D = F) approach
- The proportion of participants with HIV-1 RNA < 50 copies/mL at Weeks 12 and 24 as determined by Missing = Excluded (M = E) and Discontinuation = Failure (D = F) approach
- The number and proportion of participants who prematurely discontinued B/F/TAF by Weeks 12 and 24

Additional efficacy endpoints of this study are:

- The change from baseline in CD4+ cell counts and CD4% at Weeks 12 and 24.

6.2. Analysis of the Secondary Efficacy Endpoints

6.2.1. HIV-1 RNA ≥ 50 or < 50 copies/mL at Weeks 12 and 24 as determined by Missing=Excluded and Discontinuation=Failure approach

Number and percentage of participants with HIV-1 RNA ≥ 50 copies/mL and < 50 copies/mL by visit will be analyzed using the following 2 methods for imputing missing HIV-1 RNA:

- Missing = Excluded (M = E):

In this approach, missing data will be excluded in the computation of the percentages (ie, missing data points will be excluded from both the numerator and denominator in the computation). The denominator for percentages at a visit is the number of participants in the FAS with nonmissing HIV-1 RNA value at that visit.

- Discontinuation = Failure (D = F):

In this approach, treatment discontinuation-as-failure analysis includes participants with at least one HIV-1 RNA value within an analysis window (see Table 3-1.) and participants who discontinued B/F/TAF before the lower bound of the analysis window. All participants who discontinued B/F/TAF before the lower bound of the analysis window will be classified in the category 'HIV-1 RNA ≥ 50 copies/mL' (ie, virologic failure). Missing data in the analysis window due to the other reasons will be excluded from both denominator and numerator for D = F analysis.

For both M = E and D = F analyses, the number and percentage of participants with HIV-1 RNA in the following categories will be summarized based on the FAS:

- < 50 copies/mL
 - < 20 copies/mL
 - < 20 copies/mL Not Detectable
 - < 20 copies/mL Detectable
 - 20 to < 50 copies/mL
- \geq 50 copies/mL
 - 50 to < 200 copies/mL
 - 200 to < 400 copies/mL
 - 400 to < 1000 copies/mL
 - \geq 1000 copies/mL
 - Discontinuation (only applicable to D = F analysis)

The proportion of participants with HIV-1 RNA < 50 or \geq 50 copies/mL as defined by the 2 different missing data imputation methods will be summarized using descriptive statistics. Their 2-sided 95% CIs of the proportion will be constructed using the Clopper-Pearson Exact method.

For the D = F analysis, results will be summarized for Weeks 12, 24 and all other visits up to Week 24. For the M = E analysis results will be summarized for Weeks 12, 24 and all other visits with available data through the study.

For the D = F analysis, the proportion of participants with HIV-1 RNA < 50 copies/mL will be plotted for all visits up to Week 24 using the FAS. For the M = E analysis, the proportion of participants with HIV-1 RNA < 50 copies/mL will be plotted for all visits through the study .

